10.52 Adverse Event Submission Using Case Reports Forms (CRFs)

Submit via appropriate Alliance Case Report Forms (i.e., paper or electronic, as applicable) the following AEs experienced by a patient and not specified in Section 10.51:

- 10.521 Grade 2 AEs deemed *possibly, probably, or definitely* related to study surgery or radiation.
- 10.522 Grade 3 and 4 AEs regardless of attribution to study surgery or radiation.
- 10.523 Grade 5 AEs (Deaths)
 - 10.5231 Any death within 30 days of the patient's last study treatment or procedure regardless of attribution to study surgery or radiation.
 - 10.5232 Any death more than 30 days after the patient's last study treatment or procedure that is felt to be at least possibly study related must also be submitted as a Grade 5 AE, with a CTCAE type and attribution assigned.

10.53 Submission of Late Occurring Adverse Events

Refer to the instructions in the Forms Packet (or electronic data entry screens, as applicable) regarding the submission of late occurring AEs following completion of the Active Monitoring Phase (i.e., compliance with Test Schedule in Section 4.0).

11.0 Diagnosis of Breast Cancer Recurrence and Other Cancer Events

11.1 Local Recurrence

Local recurrence is defined as histologic evidence of ductal carcinoma *in situ* or invasive breast cancer in the ipsilateral breast or ipsilateral chest wall.

11.2 Regional Recurrence

Regional recurrence is defined as the cytologic or histologic evidence of disease in the ipsilateral internal mammary, ipsilateral supraclavicular, ipsilateral infraclavicular and/or ipsilateral axillary nodes or soft tissue of the ipsilateral axilla.

11.3 Distant Recurrence

Distant recurrence is defined as the cytologic, histologic, and/or radiographic evidence of disease in the skin, subcutaneous tissue, lymph nodes (other than local or regional metastasis), lung, bone marrow, central nervous system or histologic and/or radiographic evidence of skeletal or liver metastasis.

11.4 Second Primary Breast Cancer

Second primary breast cancer is defined histologic evidence of ductal carcinoma *in situ* or invasive breast cancer in the contralateral breast or contralateral chest wall.

11.5 Second Primary Cancer (Non-breast)

Any non-breast second primary cancer other than squamous or basal cell carcinoma of the skin, melanoma *in situ*, or carcinoma *in situ* of the cervix is to be reported and should be confirmed histologically whenever possible.

11.6 Death

Underlying cause of death is to be reported.

12.0 Descriptive Factors

12.1 Menopausal Status

Pre vs. post vs. above categories not applicable (age < or \geq 50)

- Pre is < 6 months since last menstrual period (LMP) **and** no prior bilateral ovariectomy **and** not on estrogen replacement;
- Post is prior bilateral ovariectomy **or** >12 months since LMP with no prior hysterectomy **and** not currently receiving therapy with LH-RH analogs (e.g., Zoladex))
- Above categories not applicable **and** age < 50
- Above categories not applicable **and** age \geq 50.

12.2 Time of Registration: Pre-surgery vs Post-surgery

13.0 Treatment/Follow-up Decision at Evaluation of Patient

13.1 Follow-Up After Completion of WBI

Patients will be followed as per the test schedule for 5 years after completion of WBI.

13.2 Conditions Requiring Study Termination

Patients who convert to a mastectomy for any reason within a year of initial surgery will go to the observation phase of the study. All data and forms prior to and up to mastectomy must be submitted. Tissue from the mastectomy should be submitted if possible. Patients will be followed for survival yearly for 5 years after treatment discontinuation.

Patients found to have any of the following:

- those with persistent positive margins who decline mastectomy;
- the dose constraint is not met (≤ 10 weeks of initial attempt of WBI planning in patients not receiving adjuvant chemotherapy, or ≤ 8 weeks after completion of chemotherapy for those patients receiving chemotherapy)

will have participation in the study terminated. The on-study material, surgery forms, pathology forms and the End of Active Treatment/Cancel Notification Form must be submitted. No further data submission is needed.

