13.4 Conditions Requiring Study Discontinuation

Patients who discontinue the study at any time due to any of the following:

- patient refusal to continue study tests and/or procedures
- develop disease recurrence
- administration of anti-neoplastic (non-protocol) treatment

will enter the event monitoring phase where disease and vital status will be collected yearly for 5 years after completion of WBI (or treatment discontinuation).

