13.7 Recommendations for Local Recurrence

Patients who develop local recurrence are recommended to be evaluated by having a mammogram and MRI and to undergo a mastectomy.

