16.2 Study Endpoints

The primary endpoint for this trial is the diagnosis of a local recurrence as a first event where a local recurrence is defined as histologic evidence of ductal carcinoma *in situ* or invasive breast cancer in the ipsilateral breast or chest wall.

The cumulative incidence of local recurrences will be estimated in the competing risk framework as described by Marubini and Valsecchi where regional recurrences, distant recurrences and death without a local recurrence will be considered competing risks and contralateral breast and non-breast second primary cancers will not be considered competing risk.

All eligible patients who have undergone breast conservation surgery with 2 or 3 sites of disease resected to negative margins (i.e., not converted to mastectomy or have not refused mastectomy for positive margins) will be included in the analysis of the primary endpoint.

Secondary clinical endpoints are:

- The conversion rate to mastectomy secondary to persistent positive margins; poor cosmesis within the first year of attempting breast conservation surgery (BCS); or inability to satisfy radiation dose constraints on the boost to the lumpectomy bed of each site of disease
- The type and severity of adverse effects of breast conserving surgery and radiation for women with multiple ipsilateral primary breast cancer (MIBC)
- The radiation-related side effects of whole breast radiation with a boost to 1 large or > 1 lumpectomy site
- The patient's perception of cosmesis.

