16.6 Analysis Plan

16.61 Local Recurrence Rate

All eligible patients who have undergone surgery that was not converted to a mastectomy and who did not have a finding of single contiguous area of malignancy on final pathology will be included in the analysis of the primary endpoint.

The cumulative incidence of local recurrences will be estimated in the competing risk framework as described by Marubini and Valsecchi where regional recurrences, distant recurrences and death without a local recurrence will be considered competing risks and contralateral breast and non-breast second primary cancers will not be considered competing risk. A 95 % Poisson confidence interval for the cumulative incidence of a local recurrence within 5 years will be constructed.

Gentilini *et al.* reported that cumulative incidence of local recurrence differed in terms of estrogen receptor status, HER2/neu expression, Nottingham grade, and Ki-67 expression (univariately) (Gentilini *et al.*, 2009). Gray's test will be used to explore whether the cumulative incidence of local recurrence differs with respect to these factors as well as progesterone receptor status, number of positive lymph nodes, number of foci, t-stage, age, perception of quality of life as measured by LASA at registration (poor: 0 to 3; middling: 4 to 7; good/excellent: 8 to 10), and fatigue as measured by LASA at registration (none to little: 0 to 3; some: 4 to 7; a great deal: 8 to 10).

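### The rules on conversion to mastectomy conflict and, read literally, let a first-year local recurrence treated by mastectomy leave the primary analysis set with its event

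*Combined protocol and SAP*

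**What the plan says.** Five sections bear on the point.

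- **13.2** sends "Patients who convert to a mastectomy for any reason within a year of initial surgery" to the observation phase. It asks for data and forms up to the mastectomy and then says: "Patients will be followed for survival yearly for 5 years after treatment discontinuation".
- **16.2** restricts the primary analysis to eligible women with two or three sites resected to negative margins, glossed as "not converted to mastectomy or have not refused mastectomy for positive margins".
- **16.61** defines the same set as "All eligible patients who have undergone surgery that was not converted to a mastectomy", and also leaves out women with a single contiguous malignancy. It gives no cause and no time limit for the conversion.
- **13.7** says: "Patients who develop local recurrence are recommended to be evaluated by having a mammogram and MRI and to undergo a mastectomy".
- **13.4** lists, among its reasons for discontinuation, patients who "develop disease recurrence". They enter event monitoring, where both disease and vital status are collected yearly.

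Sections 2.21, 16.2 and 16.62 describe the secondary conversion endpoint by cause: persistent positive margins, poor cosmesis in the first year, or unmet radiation dose constraints. Recurrence is not among the causes.

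**The concern.** Take a woman resected to negative margins whose local recurrence is proven histologically at month 9 and treated by mastectomy. She has had a mastectomy within a year, for a reason, so the words of 13.2 fit her. The words of 13.4 fit her too, and no precedence is stated. Under 13.2 she is followed for survival only; under 13.4 disease status is also collected. If she counts as converted, 16.61 takes her out of the primary set, and her primary event goes with her.

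A second problem remains even if conversion is read narrowly. Poor cosmesis within the first year is a listed cause. A woman may finish whole breast irradiation (WBI), be at risk for months, and then have a mastectomy for cosmesis. She is removed retrospectively, so membership of the set depends on something that happens after follow-up has begun. If her mastectomy specimen showed DCIS or invasive cancer, it would meet the wording of the local recurrence definition in 11.1, yet she would be excluded.

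Removing events biases the 5-year rate downward, towards declaring conservation acceptable. Removing women without an event raises it slightly, so the downward bias applies only where events are removed.

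**Working it through.** **Inputs from the documents.** 200 evaluable patients; success if the upper 95% limit is below 8%, stated as at most 8 first-event local recurrences (16.3); Poisson interval (16.61); benchmark 5-year rate of 5.1% from the largest retrospective series (1.1).

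**Assumption, not in the documents.** The share *f* of 5-year local recurrences that would be removed is taken as 5%, 10% or 20%. The value 20% corresponds to a constant hazard with every first-year recurrence leading to mastectomy inside the window.

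**1. Reproduce the plan's cut-off.** The exact two-sided upper limit for *x* events is U(x) = ½·χ²(0.975; 2(x+1)), divided by N.

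- 8/200: 7.88%, below 8%.
- 9/200: 8.54%, above 8%.

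The stated maximum of 8 is reproduced. A one-sided 95% Poisson limit (7.85% at 9/200) or a Wald limit (7.44%) would have allowed 9, so the exact two-sided limit is the one that matches.

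**2. Remove events together with the women.** U(8) = 0.07882 × 200 = 15.76.

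| True events | Removed | Analysed | Upper limit | Result |
|---|---|---|---|---|
| 9 | 0 | 9/200 | 8.54% | fail |
| 9 | 1 | 8/199 | 7.92% | pass |
| 10 | 0 | 10/200 | 9.20% | fail |
| 10 | 2 | 8/198 | 7.96% | pass |
| 11 | 3 | 8/197 | 8.002% | fail |

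One or two removals can reverse the conclusion. Three out of eleven do not, because the smaller denominator works the other way.

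**3. Chance of meeting the criterion.** Let μ = 200 × true rate, removed events D ~ Poisson(fμ), and remaining events R ~ Poisson((1−f)μ). Then P(pass) = Σ P(D=d)·P(R ≤ c(200−d)), where c(N) is the largest count whose limit is below 8%. This gives c = 8 for N = 198 to 200, and c = 7 from N = 197 down to 181, because U(7) = 0.07211 × 200 = 14.42 and 14.42/0.08 = 180.3.

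| True 5-year rate (μ) | f = 0 | 5% | 10% | 20% |
|---|---|---|---|---|
| 8% (16) | 2.2% | 3.3% | 4.5% | 7.9% |
| 5.1% (10.2) | 31% | 37% | 42% | 52% |

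Expected removals are 0.8, 1.6 and 3.2 events at 8%, and 0.5, 1.0 and 2.0 at 5.1%. The model treats the 5-year count as Poisson with complete follow-up, as the plan's sample-size section does.

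**4. How many recurrences could fall in the window?** Without chemotherapy, WBI starts by about week 10 after surgery (7.63) and lasts about 6 weeks (4.1, footnote 13), so it ends near week 16. The first surveillance mammogram is a year later, near week 68, outside the one-year window. The first six-monthly visit falls near week 16 + 26 = 42, about month 10, inside it. The window is therefore not empty, but routine imaging does not fall within it. Chemotherapy shifts both dates later.

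**The case against.** A reader might infer that the plan deletes first-year events by rule. It does not say so. Section 13.2 assigns a follow-up phase and does not mention an analysis set. No sentence calls a mastectomy for recurrence a conversion, although none says that it is not. Mastectomy after recurrence is recommended, not required.

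A reader might also take 13.2 as the only text on conversion. It is not. Sections 2.21, 16.2 and 16.62 give causes, and the futility rule in 16.51 names margins or cosmesis with a six-month window. Section 16.2 attaches the exclusion to margin status, and 16.61 speaks of surgery being converted, which most naturally means the conserving operation. Recurrence has its own route in 13.4, and recurrence forms are scheduled in 18.2. The event would be recorded.

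All of this stands as evidence of intent. It does not settle the text. The cause lists define a secondary endpoint, while 13.2 applies to any reason, and neither exclusion sentence refers to the lists. Section 16.61, the analysis section, lacks the margin qualifier found in 16.2. The separate route in 13.4 creates a second instruction for the same woman. Recording an event does not place her in the primary set.

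It can also be argued that analysing only women whose breast was conserved is a legitimate choice of population. That is fair for conversions before WBI is complete. It is weaker for women who had completed conservation treatment and were already at risk.

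**Conclusion.** The sections conflict, and the conflict reaches the primary set and the counting of primary events. On the literal text, a first-year histologic local recurrence treated by mastectomy can be removed; the cause lists suggest that this was not meant. The number of women is probably small, and the documents give no first-year rate.

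The matter still deserves correction because one or two events can decide the trial. Under the assumed 5–20% share, the chance of meeting the criterion rises from 2.2% to 3.3–7.9% at a true 8%, and from 31% to 37–52% at a true 5.1%. The upper ends need a constant hazard and mastectomy within the window in every case, so they are outer values. Holding the denominator at 200 would give 10.9% and 57% at the 20% share, but that is not a fair calculation, because removed women leave the denominator as well.

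The retrospective removal of first-year cosmetic mastectomies is a defect under either reading. Its direction depends on whether those women had an event.

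**What to change.** - In 16.2 and 16.61, define the excluded conversions by the causes in 2.21, with no prior or concurrent histologic local recurrence, and only where the conversion precedes completion of WBI.
- State that a histologic local recurrence after margin-negative conservation is a primary event and stays in the denominator, whatever surgery follows. Use the same definition for the count of local recurrences in 16.51.
- Keep women who completed WBI and later have a mastectomy for poor cosmesis in the set, censored at the mastectomy date. This assumes that the decision is unrelated to recurrence risk, which should be stated.
- Reconcile 13.2 with itself (observation phase against survival-only follow-up) and with 13.4, and say which applies to a woman who meets both.

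The cost is wording in these sections, settled before the analysis. Recurrence forms are already collected, and 13.2 already asks for data up to the mastectomy, so no new data are needed. The estimate may become slightly less favourable.

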7. Adverse events are to be recorded from the start of the first surgery to 30 days after the last surgery performed.
8. For patients who consent, either paraffin-embedded OR frozen tissue will be submitted within 30 days following surgery (see Section 14.0 for details).
9. Active Monitoring patient questionnaire booklets will be administered to patients at the following timepoints: 5 to 30 days following final surgery (initial post-operative visit); every six months (\pm 1 month) for the first 2 years following completion of WBI; then yearly (\pm 2 months) for the next 3 years.
10. Surgeon questionnaire booklets will be completed by the patient's surgeon 5 to 30 days following final surgery (initial post-operative visit) to assess cosmetic outcome.
11. Adjuvant chemotherapy is at the discretion of the study physician and should begin within 12 weeks following surgery.
12. Performance status is completed prior to the start and at the end of adjuvant chemotherapy.
13. WBI is performed daily, one session every day, typically Mondays to Fridays for about 6 weeks. See Section 7.6 for details.

14. Performance status is completed prior to the start and at the end of WBI.
15. The radiation plan and standard radiation treatment summary must be submitted to IROC Rhode Island (QARC) for central review. Treatment plan documents are available on the website at [REDACTED]
16. Observation will be every 6 months (\pm 1 month) for 5 years beginning at the end of WBI.
17. First observation mammogram should be done at 1 year following completion of WBI, then yearly after that (i.e., at 1, 2, 3, 4 and 5 years, \pm 2 months) for a total of 5 years.

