13.5 Definition of Ineligible

A patient is deemed *ineligible* by the data center if, after registration, it is determined that at the time of registration, the patient did not satisfy each and every eligibility criteria for

study entry.

- If the patient did undergo surgery with/without radiation, submit all treatment/intervention forms and the Off Treatment/Cancel Notification Form.
- If the patient did not undergo surgery, submit on-study material and the Off Treatment/Cancel Notification Form. No further data submission is necessary.

Note: If, after a site has registered a patient into the study, the site becomes aware of information that questions the patient's eligibility for the study, the site should contact the QAS/Data Manager at the telephone number and/or email address listed on the Protocol Resources page of the protocol.

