18.2 Submission Timetable

Study phases	
Surgery	Day of the registration to 30 days post the final surgery
Adjuvant chemotherapy	Day of evaluation prior to the start of hormone medications or adjuvant chemotherapy to the day of evaluation following completion of hormone medications or adjuvant chemotherapy
WBI	Day of evaluation prior to the start of WBI to day of evaluation following completion of WBI
Observation ¹	Six months after the completion of WBI to 5 years after the completion of WBI

1. Patients will go to observation for refusal, adverse events or at the discretion of the treating physician. Patients who have recurrence during treatment or during the observation phase and patients who refuse to comply with the test schedule during the observation phase will enter the event monitoring phase (see Section 13.4).

Initial Material(s)

Case Report Form (CRF)	Active-Monitoring Phase (Compliance with Test Schedule Section 4.0)
Institution Contact Information	
On-Study ¹	
On-Study: Mammography	
On-Study: MRI ² (if performed)	
On-Study: Ultrasound ³	
On-Study: Biopsy Information	
Adverse Events: Baseline	
Imaging Submission: Institution	≤ 2 weeks after registration
Report Submission ⁴	
Reports – Biopsy Procedure, Biopsy Pathology, Mammography and MRI (if performed)	
Ultrasound (if performed)	
Note: The distance between the lesions must be documented on mammogram and/or MRI.	
Blood Sample Submission: (Institution)	
Patient Status: Baseline	
Patient Questionnaire Booklet- Baseline	≤ 2 weeks after registration – The Patient Questionnaire Booklet must be ordered by the site using the CTSU request form located on the CTSU website
Patient Questionnaire Booklet - Compliance	≤ 2 weeks after registration - This form must be completed only if the Patient Questionnaire Booklet contains absolutely NO patient provided assessment information.
Off Treatment	Submit ≤ 2 weeks after registration if withdrawal/refusal occurs prior to surgery

1. The Breast Lesion Position Diagram must be completed for each patient and uploaded into Rave with the On-Study form. Note: Lesions should be numbered clockwise per the breast diagram completion instructions.
2. This form will be required if an MRI was performed.
3. This form will be required if an ultrasound was performed.
4. This form is used to record the submission of the baseline reports needed for review by the QAS/Data Manager.

Test Schedule Material(s)**CRF****Active-Monitoring Phase**

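### Section 13.2 ends data submission for terminated women without naming an adverse event form, in conflict with the rule to record events until 30 days after the last surgery

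*Combined protocol and SAP*

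**What the plan says.** Section 13.2 ends study participation for two groups. The first is "those with persistent positive margins who decline mastectomy". The second is women in whom the whole-breast radiation dose constraint is still unmet at the end of the time allowed. For both it states: "The on-study material, surgery forms, pathology forms and the End of Active Treatment/Cancel Notification Form must be submitted", followed by "No further data submission is needed". No adverse event form appears in the list.

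Other parts of the protocol set a wider duty:

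- Table 4.1 footnote 7, for women registered before surgery: "Adverse events are to be recorded from the start of the first surgery to 30 days after the last surgery performed".
- Section 18.2 defines the surgery phase as "Day of the registration to 30 days post the final surgery". It marks Adverse Event and Other Adverse Event in that phase as forms of their own, next to Surgery and Pathology Information.
- Section 10.51 has wound infection, postoperative hemorrhage, seroma and lymphedema graded at each post-surgery evaluation. Section 10.52 adds, for other events, related grade 2 events and all grade 3 and 4 events. Neither makes an exception for terminated women.

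Women who convert to mastectomy within a year come under a different sentence of 13.2: "All data and forms prior to and up to mastectomy must be submitted".

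**The concern.** The type and severity of adverse effects of breast-conserving surgery is a secondary goal (2.25) and a secondary endpoint (16.2, analyzed under 16.64). A site that treats the 13.2 list as complete would send no adverse event form for a terminated woman. A site that follows footnote 7 and Section 10 would send one. Both could claim to be following the protocol, so what is collected would depend on the site.

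The women affected are those in whom conservation did not succeed. Under 7.2, re-excision is done as needed to clear margins, so those left with positive margins are likely to include re-operated women. Section 16.64 names no analysis population for adverse events. Nothing in the plan therefore says whether a terminated woman without an event form is left out of the denominator or counted as having had no event.

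**Working it through.** The plan states no figure on this point, so there is none to reproduce. The check is mainly a comparison of texts.

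**Step 1. The rules side by side.**

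| Place | Applies to | Adverse event data asked for |
|---|---|---|
| 13.2, form list | Terminated women | No event form named; submission then ends |
| Table 4.1, footnote 7 | Women registered before surgery | First operation to 30 days after the last |
| 10.51 | No exception stated | Four surgical events graded at each post-surgery evaluation |
| 10.52 | No exception stated | Other events: related grade 2, all grade 3 and 4, on case report forms |
| 18.2 | No exception stated | Two event forms in a phase lasting to 30 days after final surgery |

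The first row cannot be followed to the letter together with the others. Table 4.2, for women registered after surgery, has no adverse event row, so the conflict with footnote 7 is confined to women registered before surgery.

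**Step 2. Who can be terminated while the 30 days are still running.**

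- *Dose constraint not met.* Without chemotherapy, 7.634 sets the limit at 10 weeks from the last surgery: 10 × 7 = 70 days, which is beyond 30. With chemotherapy, the limit is 8 weeks after chemotherapy ends (7.622). The window has normally closed by then. What could still be missed is a form not yet sent. As the table reads in the available text, the event forms in the surgery-phase column of 18.2 carry no submission deadline, whereas the Surgery form is due within 30 days.
- *Positive margins, mastectomy refused.* If termination comes d days after the last operation, 30 − d days remain. The documents do not give d. If the final margin result takes 7 to 14 days (assumption), at most 30 − 14 = 16 to 30 − 7 = 23 days remain, and fewer once time for the decision on mastectomy is added. On the literal list, events before termination that have not yet been sent would be dropped too.

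**Step 3. Which events depend on the omitted forms.** Serious events go through expedited reporting (10.4), and 10.11 requires every expedited event to be reported routinely as well. By the table in 10.4, grade 1 and 2 events without hospitalization need no expedited report. Low-grade wound infection, seroma, hemorrhage and lymphedema therefore rest on the case report forms.

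**Step 4. Illustration of size (all inputs assumed except the 265).** Let t be the share of women terminated without event forms, p the event rate in the others, and R the ratio of risk in the terminated women.

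- True rate = (1 − t)p + tpR.
- Observed rate if they are left out = p, so the shortfall is tp(R − 1).
- Observed rate if they are counted as event-free = (1 − t)p, so the shortfall is tpR.

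Take 3 to 10 women of the target 265 (t = 3/265 = 1.13% to 10/265 = 3.77%), p = 10% and R = 1 to 3.

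- Left out: from 1.13% × 10% × 0 = 0 to 3.77% × 10% × 2 = 0.75 percentage points.
- Counted as event-free: from 1.13% × 10% × 1 = 0.11 to 3.77% × 10% × 3 = 1.13 percentage points.

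With a wider assumption of t = 2% to 10%, the true rate is 10.0% to 12.0%, against 10.0% observed if they are left out, or 9.8% down to 9.0% if counted as event-free. The extreme corner (t = 10%, R = 3) gives 12.0 − 9.0 = 3.0 points. If R were below 1, say 0.5, leaving them out would raise the observed rate: 3.77% × 10% × (0.5 − 1) = −0.19 points of shortfall. All these figures treat every event in these women as lost, which overstates the effect given step 3.

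**The case against.** **The list may already include the event forms.** The phrase for surgery forms is plural and undefined, and 18.2 places both adverse event forms in the surgery phase. This reading is possible but strained. Pathology Information is also a surgery-phase form, and 13.2 names it separately, which would be needless if the phrase covered the whole phase. Even if the phrase is merely ambiguous, the text should be settled.

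**The duties in Section 10 stand regardless.** This is correct, and it limits the point. Footnote 7, 10.52, 10.4 and 10.11 exempt nobody, and a site may well follow them. What remains is a conflict between provisions, not a demonstrated loss.

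**Three stronger readings are tempting, and the documents do not support them.**

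- *A reader might infer that surgical morbidity is lost in re-operated women and that the complication rate is therefore too low.* Women with an unmet dose constraint need not have been re-operated and are usually past the 30 days. Women re-operated by mastectomy are not under this list. Serious events still arrive. The documents give no event risk for terminated women, and without a denominator in 16.64 the direction of any bias is open.
- *A reader might infer that the cut-off for converters lowers the breast-conserving complication rate.* For them the last surgery is the mastectomy, so the cut-off in 13.2 does fall short of footnote 7. But events after a mastectomy follow a different operation and lie outside the stated endpoint.
- *A reader might infer that more is asked of an ineligible woman than of an eligible one.* Section 13.5 says: "If the patient did undergo surgery with/without radiation, submit all treatment/intervention forms and the Off Treatment/Cancel Notification Form". It too names no adverse event form, its key phrase is undefined, and 18.2 has a form with a similar title (Patient Status: Treatment (Intervention)). The comparison holds only if one vague phrase is read broadly and the other narrowly.

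**Conclusion.** The conflict is real and stands in the current text. Read literally, 13.2 allows non-serious surgical adverse events to go unreported, mainly in women registered before surgery whose margins stay positive, who refuse mastectomy, and who are terminated within 30 days of their last operation. The primary endpoint is unaffected.

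The size and direction of any effect on the secondary endpoint cannot be determined, because the documents give no count of terminated women, no surgical event rate and no adverse event denominator. It is likely small: about 1 percentage point or less on the narrower assumptions above, and larger only if many more women are terminated. The conclusion rests on 13.2 being applied as written; the documents do not show that any site has done so. This is a modest point, worth correcting because the correction is nearly free.

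**What to change.** In 13.2, add the Adverse Event and Other Adverse Event forms, covering the period through 30 days after the last study surgery, to the list for terminated women. Reword the closing sentence so that data submission ends only after that date.

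For converters, reconcile the cut-off at mastectomy with the footnote 7 window. If events after the mastectomy are collected, report them separately from those of breast-conserving surgery.

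The cost is a small wording change in 13.2 and one or two existing forms for a few women. Treatment and the primary analysis do not change.
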